## **7.0 Study Design and Procedures**

### **7.1 Study Design**

[figure not shown]
This will be a single-center, open label, non-randomized Phase 0 feasibility trial to determine the neuro-pharmacokinetic/pharmacodynamic profile of posaconazole for HGGs. We will enroll 10 (5 for study group and 5 for control group) evaluable patients over 12 months with recent MRI findings suggestive of

high grade gliomas with need for surgical resection. Our historical surgical volume supports the feasibility of this proposal.

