### 8.2 Sample size determination

#### Design

This is an exploratory (pilot) study to assess whether posaconazole can penetrate brain tissue at sufficient enough levels to result in expected downstream biological effects on glycolysis and tumor cell survival. Five evaluable patients will be studied for this trial. The sample size justification is not based on statistical rationale but clinical affordability.

The following metrics will be used to define success and support the decision to proceed with advanced phase trials:

- Detection of  $\geq 5\mu\text{M}$  concentration of either drug in resected tumor in at least 2 of 5 patients in each arm – a value that is within the range needed to achieve efficacy for CNS fungal infections and to achieve 50% glioma tumor cell kill *in vitro* based on our prior published report (ref 58); AND
- Reduction in average lactate and pyruvate concentrations in both resected tumor and dialysate fluid (using MDCs) in the treated cohorts compared to controls; AND
- Steady concentration of lactate and pyruvate over 24 hours of monitoring with MDCs in control participants.

The rationale for the above is based on the notion that any tumor penetration by drug, with concomitant effect on glycolysis, warrants further in-depth analysis as our therapeutic options for these deadly tumors are currently very limited. Intra-tumoral drug concentration on the lower range would still be promising and warrant dose-escalation studies, as the currently selected dosing is based on anti-fungal regimens that are known to be safe. Phase II studies for assessing tumor response would be warranted if substantial tumor penetration together with expected biological effect is observed. A negative trial would nonetheless have value as it would serve as an efficient means of determining whether or not either of ketoconazole or posaconazole hold promise against GBMs, as part of a “fail early” approach to drug-development, while minimizing the human and financial cost investment.

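### Section 8.2 says a negative trial determines whether ketoconazole or posaconazole holds promise; with 5 versus 5 patients, descriptive analysis and no ketoconazole patients, the design cannot support that.

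*Combined protocol and SAP*

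**What the plan says.** Section 7.1 describes a single-center, non-randomized Phase 0 feasibility trial: "We will enroll 10 (5 for study group and 5 for control group) evaluable patients over 12 months". Section 8.2 calls the study exploratory and says of its size: "The sample size justification is not based on statistical rationale but clinical affordability".

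Section 8.2 then lists three criteria joined by AND, introduced by "The following metrics will be used to define success and support the decision to proceed with advanced phase trials":

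- Metric 1: a tumor drug level of at least 5 µM "in at least 2 of 5 patients in each arm".
- Metric 2: "Reduction in average lactate and pyruvate concentrations in both resected tumor and dialysate fluid (using MDCs) in the treated cohorts compared to controls".
- Metric 3: "Steady concentration of lactate and pyruvate over 24 hours of monitoring with MDCs in control participants".

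The paragraph after the list makes two statements about disappointing results. It says that tumor concentrations in the lower range would still be promising and would justify dose-escalation studies. It also says of a negative trial that "it would serve as an efficient means of determining whether or not either of ketoconazole or posaconazole hold promise against GBMs", and places this within a fail-early approach to drug development.

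Section 8.3 plans descriptive statistics only. It sets no margin, interval or error rate for any of the three metrics. Section 2.3 says that the ketoconazole study is a separate protocol.

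**The concern.** The only definition of a negative trial that the plan offers is failure to meet the three metrics. Failing them in five treated and five control patients is weak evidence that an effect is absent, because chance alone will often produce it when the drug works. Metric 2 is the most exposed: it requires "Reduction in average lactate and pyruvate concentrations in both resected tumor and dialysate fluid", which is four comparisons that must all point the same way, so noise in any one of them makes the trial negative. Nothing in 8.3 would show the reader how large an effect remains compatible with the data.

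The sentence fixes in advance how a failed result will be read. At stake is a conclusion that posaconazole lacks promise when the data cannot separate no effect from a moderate one. The sentence also extends that conclusion to a drug that nobody in this trial receives.

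**Working it through.** The plan gives no alpha, power, effect size or SD, so it has no figure to reproduce.

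**Inputs from the documents.** Five per group (7.1); at least 2 of 5 at 5 µM or more (8.2, metric 1); four means all lower than control (8.2, metric 2).

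**Assumptions, none of them in the documents.** Normally distributed outcomes with equal SD in the two groups; the true reduction in SD units, taken as equal for all four measures; the correlations among the four comparisons; and the true share of patients reaching 5 µM.

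**Metric 2.** A difference of two means with five per group has standard error √(2/5) = 0.632 SD. For a true reduction of d SD, the chance that one treated mean is lower is Φ(d/0.632).

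- At d = 0.5: 0.5/0.632 = 0.791 and Φ = 0.785, so a single comparison is missed 21.5% of the time.
- Four perfectly correlated comparisons act as one: miss 21.5%.
- Four independent comparisons: 1 − 0.785⁴ = 61.9%.
- In between, the probability comes from the four-dimensional normal distribution. Three middle structures were used, with correlation within a matrix (tumor or dialysate) and across matrices as shown:

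| Within / across | Miss at 0.5 SD | Miss at 1 SD | Miss at 1.5 SD |
|---|---|---|---|
| 0.5 / 0.3 | 50.6% | 17.5% | 3.2% |
| 0.7 / 0.5 | 44.2% | 15.1% | 2.8% |
| 0.9 / 0.7 | 36.6% | 11.9% | 2.2% |

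**Metric 1.** With true reach rate p, P(0 or 1 of 5) = (1 − p)⁵ + 5p(1 − p)⁴.

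- p = 0.4: 0.078 + 0.259 = 0.337
- p = 0.5: 0.031 + 0.156 = 0.188 (rounded from 0.1875)
- p = 0.6: 0.010 + 0.077 = 0.087
- p = 0.7: 0.031; p = 0.8: 0.007

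**What 0 of 5 excludes.** The exact upper limit solves (1 − p)⁵ = α.

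- One-sided 95%: 1 − 0.05^(1/5) = 45.1%
- Two-sided 95%: 1 − 0.025^(1/5) = 52.2%
- One-sided 90%: 1 − 0.10^(1/5) = 36.9%

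One of five also fails metric 1; its one-sided 95% upper limit is 65.7%.

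**Precision of one mean difference.** The 95% CI half-width is t(0.975, 8 df) × √(2/5) = 2.306 × 0.632 = 1.46 SD.

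**Metric 3.** Steady is not defined, so its failure rate cannot be computed. Because the metrics are joined by AND, it can only add to the misses.

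**The case against.** The strongest reply is that this is openly a pilot sized by affordability. Descriptive analysis is normal in Phase 0, and a screen meant to keep only large effects may accept missing small ones. Nothing in the documents makes 0.5 SD the relevant effect, and at 1.5 SD metric 2 is rarely missed. Likewise, 2 of 5 is an observed cut-off; the plan does not say that a true 40% is adequate, and at a true 70% or 80% metric 1 seldom fails. All of this stands as a defence of the design. It does not defend the sentence, because a pilot of this kind is exactly what cannot settle whether a drug holds promise.

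A reader might infer three stronger things that the documents do not support.

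- *That the success rule as a whole misses a real effect 37% to 51% of the time.* Those figures belong to metric 2 alone, under an assumed 0.5 SD effect and middle correlations. Adding metric 1 at a true reach rate of 40%, treated as independent, gives a pass rate of 0.663 × 0.494 = 33% to 0.663 × 0.634 = 42%. Other reach rates give other figures, and metric 3 is left out.
- *That 0 of 5 can never exclude a 40% reach rate.* This holds at the 95% level, one- or two-sided, but not at one-sided 90%, where the limit is 37%.
- *That posaconazole would be dropped.* The metrics support a decision to proceed; no rule abandons the drug. For low tumor levels, 8.2 itself points to dose escalation. That text covers a shortfall on metric 1 only. It says nothing about a failure on metric 2, and it sits uneasily beside the negative-trial sentence in the same paragraph.

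**Conclusion.** The sentence in 8.2 claims more than the trial can deliver. The exact miss rate depends on inputs that the plan does not supply, so no single percentage is a property of the design. At an assumed 0.5 SD reduction, metric 2 is missed in at least about one trial in five, even in the most favourable case of perfectly correlated measures, and in up to 62% if they are independent. At the 95% level, the worst possible result on metric 1 still allows a reach rate of 45% (one-sided) or 52% (two-sided). Large effects, of about 1.5 SD, would usually be seen on metric 2.

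The ketoconazole part needs no assumption: this trial has no ketoconazole patients, so its result cannot determine that drug's promise.

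This is a fault in the stated interpretation of a negative result. It does not show that the trial is too small for its exploratory purpose.

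**What to change.** In 8.2, replace the negative-trial sentence with wording such as: *Failure to meet the criteria will be reported as criteria not met for posaconazole at this dose with 5 patients per group; it will not by itself be taken as evidence that posaconazole lacks effect.* Remove ketoconazole from the sentence. Reconcile it with the statement on lower-range tumor concentrations, so that a low-concentration result has one stated reading.

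In 8.3, add the share of treated patients at or above 5 µM with its exact 95% CI, and each of the four treated-minus-control differences in lactate and pyruvate with its 95% CI. State the confidence level wherever a limit is quoted. The intervals for the differences will be wide (half-width about 1.46 SD), which is the information that a reader of a negative result needs.

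The cost is a few sentences and five intervals, with no added patients, samples or procedures. The downside is a less favourable claim for what a negative result shows.

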### **Study Population**

Only patients who are eligible and take posaconazole according to protocol specifications (study drug arm only) **and** have undergone successful MDC implantation will be considered evaluable and included in the study analysis. Otherwise, enrolled patients will be replaced. All eligible patients for whom analyzable dialysate samples were obtained for at least 7 of the 9 time points will be considered evaluable for the primary study endpoint. Patients who are not evaluable will be replaced.

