### **3.3.2 Follow-up for withdrawn subjects**

The PI will complete all end of treatment procedures when a participant withdraws from treatment. All participants who discontinue treatment secondary to an AE will be followed until resolution, stabilization or return to a baseline condition. Participants who fail to complete treatment for reasons other than AE or unacceptable toxicity may be replaced.

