### **Study drug group**

Participants will be given 12 days' worth of the study drug (pills) and verbally instructed how and when to take them. The prescription bottle will have a label with this information on it as well.

The timing of study drug administration will be based on the scheduled date and time of biopsy or surgery, which will occur within 7-10 days of Visit 1. The latter parameter is based on the drug half-life, as follows:

- Participants will be taking posaconazole as 300mg PO BID in the first day, followed by 300mg PO once daily thereafter.
- The mean elimination half-life of posaconazole is 26-31 hours (product monograph). Therefore, posaconazole will reach steady state at approximately 130-155 hours following the first dose (5 half-lives). As such, we will work backwards from the scheduled date and time of biopsy or surgery such that participants in the posaconazole arm will receive drug for 168-240 hours. The upper range of the dosing (240 hours) is to minimize potentially unnecessary exposure to drug while accounting for variability in half-life measurements.

In order to maintain steady-state concentrations, study drug will be administered at the following times as well:

1. Pre-operatively on the morning of the planned surgical intervention
2. On the morning of postoperative day 1, at 8:00AM +/- 4 hours \*

\*Only if postoperative CT rules out complications and the MDC(s) are correctly positioned.

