#### **Intra-operative procedure**

##### **Assessments common to both control and study drug groups**

After surgical resection, frozen pathology will be reviewed to verify the diagnosis of HGG. Once pathology has been verified, and it is determined there is adequate tissue for clinical diagnosis, we will take our research sample will be taken and prepared for assessment of intra-tumoral drug concentration (study drug arm only) and assessment of HK2 activity, downstream glycolysis metabolites, tumor cell proliferation, and angiogenesis.

Where an open surgical resection has been planned, one (1) tissue sample will be from the center of the tumor and one (1) from the tumor capsule and snap-frozen immediately in the operating room (<15 minutes). No individual sample will be greater than 1cm x 1cm. These will then be divided for individual research-specific analyses.

As noted below for postoperative plasma collection schedule, blood samples will be obtained at the time of tumor sampling as well to determine and compare tumor: blood drug concentration ratios. The exact time of tumor resection and blood sampling will be recorded.

For patients in whom the intraoperative diagnosis is not consistent with HGG, no additional blood will be drawn and the patient will not be able to continue study and will be considered a

screen fail. Furthermore, no MDC will be inserted. Surgical procedures necessary for the management for the particular diagnosis will be undertaken as per standard protocol for the surgeon.

Upon satisfactory resection of tumor bulk, the neurosurgeon will place two CMA 70 MDCs with Gold Tip - (ref. no. P000050, CMA, Solna, Sweden) with a membrane length of 10mm, and shaft length 100mm - in accordance with pre-op MRI. For patients with a subtotal resection of enhancing tumor, one MDC will be placed in a contrast enhancing area of the tumor and another will be placed in a non-contrast enhancing region (normal brain) within 5mm of tumor resection cavity. For patients with a complete resection of contrast-enhancing tumor, only one MDC will be placed in the non-enhancing tumor resection boundary, within 5mm of resection cavity. Ultimately, the decision on number of catheters inserted will be at the discretion of the surgeon. Upon completion of the surgical procedure, the wound will then be irrigated and closed in standard fashion and lastly the catheter will be anchored to the scalp with sutures and sterile dressings.

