### **Off Study Criteria**

Follow-up for this protocol will be considered complete when: (1) intraoperative pathology not consistent with glioma; (2) the patient dies; (3) the patient refuses posaconazole during the preoperative steady-state dosing period; (4) misses more than 3 doses; or (5) completes the 14 +/- 7 day follow-up after surgical resection of tumor. If a drug/ procedure-related complication has occurred, the patient will be clinically followed and managed accordingly until resolution.

Patients' disposition will be summarized in the following manner:

- The number and percentage of patients selected, included, completed, withdrawn and lost to follow-up will be summarized using descriptive statistics.
- Major protocol deviations will be summarized.
- The reason for withdrawal (adverse events, major protocol deviation, non-medical reason) will be summarized.

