## 18.2 Recording of Adverse Events

Subjects will be encouraged to spontaneously report any AE. Study personnel will ask open-ended questions to obtain information about AEs at every visit. Date and time of onset and resolution (if applicable) of the AE will be documented. All AEs occurring after the initiation of the study treatment (treatment emergent adverse events) will be reported, including events present at baseline that worsened during the study.

Safety will be assessed by the investigator in the form of evaluation of adverse events and clinical laboratory results and derived as data sets and frequency methods, recorded for this study. AEs by severity and causality as described below:

- Laboratory evaluations including liver function tests. Laboratory values within 1.5x the institutional upper limit of normal are considered acceptable and not as AEs

To monitor any risk of increased surgical complications associated with posaconazole, the treating surgeons will make a Note-to-File recording any unexpected events that occurred during surgery.

Patients unable to tolerate posaconazole due to AE grade 3-4 (hepatic, gastroenterological, and/or renal toxicity) will have a dose reduction. Posaconazole will be reduced to 33% of schedule dose (200 mg per dose, see table below). If the AE does not resolve within 24 hours, it will be discontinued. However, tumor tissue will still be collected and analyzed.

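### Section 8.2 makes a working catheter a condition for every analysis, so valid tumour-tissue data can be dropped, and its replacement rule does not match Section 3.3.2

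*Combined protocol and SAP*

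**What the plan says.** **Analysis population.** Section 8.2, Study Population, sets two conditions: dosing as the protocol specifies (study drug arm only) and successful placement of the microdialysis catheter (MDC). Only patients who meet the first and "have undergone successful MDC implantation will be considered evaluable and included in the study analysis" count. For the rest: "Otherwise, enrolled patients will be replaced". A further test concerns the primary endpoint alone and reads, in part: "analyzable dialysate samples were obtained for at least 7 of the 9 time points will be considered evaluable for the primary study endpoint".

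**Order of events.** Under Section 7.2.3, research tissue is taken once frozen pathology confirms HGG and enough tissue remains for diagnosis. The catheter comes afterwards: "Upon satisfactory resection of tumor bulk, the neurosurgeon will place two CMA 70 MDCs with Gold Tip".

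**Withdrawals.** Section 3.3.2: "Participants who fail to complete treatment for reasons other than AE or unacceptable toxicity may be replaced". Section 18.2, on patients whose drug is stopped because toxicity has not resolved: "However, tumor tissue will still be collected and analyzed". The Off Study Criteria in Section 8.3 end follow-up for a patient who "misses more than 3 doses".

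**Laboratory values.** Sections 7.2.2, 7.2.5 (study drug group) and 18.2 say that results up to 1.5 times the upper limit of normal (ULN) are not adverse events. In 7.2.2 and 7.2.5 the panel includes electrolytes, renal function and liver function.

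**The concern.** One sentence in Section 8.2 ties every analysis to a device that only the dialysate endpoints use. The first success metric in the same section is tumour drug concentration, and most pharmacodynamic endpoints are tissue assays. In an arm of five, each tumour set aside is a sizeable part of the evidence. The condition binds the control arm too, so a failed control catheter would also remove a tissue comparator.

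Replacement is the second problem. Section 8.2 makes it mandatory whatever the reason. Section 3.3.2 makes it optional and mentions only reasons other than toxicity. The two sections can lead to different handling of the same patient.

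The laboratory wording is a separate and smaller matter. Tolerability by adverse-event grade and frequency is the first secondary endpoint (Section 1.3), and Section 10.0 lists abnormal blood salts among the common effects of the drug. An exemption with no lower bound could keep low electrolytes out of the adverse-event counts.

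**Working it through.** **1. The plan's own figures.** Section 7.1 gives 5 + 5 = 10 evaluable patients, and Section 8.1 enrols ten. The two agree only if nobody is replaced. Section 8.2 states that the number has no statistical basis, so there is no power calculation to reproduce. The first success metric is 2/5 = 40% of patients at or above 5 µM.

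**2. Which endpoints need a catheter?**

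| Endpoint | Section | Catheter needed? |
|---|---|---|
| Posaconazole AUC0-24 in brain interstitium | 1.2, 8.3 | Yes |
| Lactate and pyruvate in dialysate | 1.3, 8.2, 8.3 | Yes |
| Tumour drug level | 8.2 | No |
| HK2 activity | 1.3, 8.3 | No |
| Glycolysis metabolites in tumour | 8.2, 8.3 | No |
| Ki-67, TUNEL, VEGF | 1.3 (8.3 by concept) | No |

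Four of the six rows do not use the catheter, and their tissue is already in hand when it is placed.

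**3. What leaving tumours out can do.** Let x of the five evaluable patients reach 5 µM, and let k further treated patients have assayable tissue but fail a condition. The all-tissue proportion then lies between x/(5+k), if none of the k reach 5 µM, and (x+k)/(5+k), if all do.

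| k | Evaluable result | Lower bound | Upper bound |
|---|---|---|---|
| 1 | 1/5 = 20% | 1/6 = 17% | 2/6 = 33% |
| 1 | 2/5 = 40% | 2/6 = 33% | 3/6 = 50% |
| 2 | 1/5 = 20% | 1/7 = 14% | 3/7 = 43% |
| 2 | 2/5 = 40% | 2/7 = 29% | 4/7 = 57% |

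These are exact limits for an assumed k. The documents give no rate of catheter failure or of non-adherence.

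**4. Replacement, side by side.** Take one patient stopped for toxicity. Section 8.2, if it treats that patient as not evaluable, requires a substitute. Section 3.3.2 permits replacement for other reasons and is silent on this one. Section 18.2 says the tissue is analysed. No sentence says which of these governs.

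**5. What the two conditions mean.** For dosing, the nearest number is the off-study limit of more than three missed doses, which is not linked to evaluability. A patient with one to three missed doses is on study but may or may not count. For the catheter, the material exists elsewhere: the correct-position requirement in 7.2.1, the malposition and haemorrhage text in 7.2.4, and the imaging confirmation before collection in 7.2.5. Section 8.2 cites none of them.

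**6. Laboratory rule.** The exemption holds whenever a value is no more than 1.5 × ULN. Any value below the lower limit of normal is below ULN, hence below 1.5 × ULN, and so is exempt. Section 18.3 asks the investigator to judge whether an abnormal result is an adverse event; a blanket exemption pre-empts that judgement. Section 8.3 describes laboratory data by CTCAE v5.0, so the values are still reported. Only the adverse-event counts are affected.

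**The case against.** The best defence is that this is a descriptive pilot with no inferential sample size, and that a sensible reader would let specific text override general text. Section 18.2's tissue instruction could be taken to control over 8.2. A dose-reduced patient is following the protocol's own reduction scheme and so naturally qualifies. The catheter condition is largely settled by the imaging text in 7.2.1, 7.2.4 and 7.2.5. On the laboratory rule, Section 8.3 describes laboratory abnormalities separately from adverse events, so nothing disappears from the report.

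Much of this stands. What is missing on the catheter is mainly a cross-reference. The clash with 18.2 is narrow: it concerns patients stopped for toxicity, and analysed there might mean only assayed. The defence does not cover a catheter failure in a fully dosed patient, for whom no specific text rescues the tissue data.

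A reader might go further in four ways that the documents do not support:

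- *Toxicity patients vanish from safety.* Section 3.3.1 puts everyone with at least one dose in any safety analysis.
- *Adverse events stop being recorded 24 hours after the last dose.* The text that follows in Section 9.1 extends recording to the 14-day visit.
- *A toxicity stop leaves four evaluable patients, so the 2-of-5 criterion is read on four.* Section 3.3.2 bars such replacement only by implication, and Sections 7.1 and 8.2 both aim for five evaluable patients.
- *Three missed doses are a fixed share of the course.* Section 7.2.1 says "participants in the posaconazole arm will receive drug for 168-240 hours", while Section 7.4.6.3 starts dosing about 130-155 hours before surgery. No single share follows until those passages are reconciled.

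**Conclusion.** The point holds in three limited parts and should be corrected.

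- **Tissue.** Read literally, Section 8.2 discards valid tumour data when a catheter fails. With one tumour left out, 2/5 could be 33% to 50% of all tissue; with two, 29% to 57%. This is a loss of information. Nothing in the documents shows whether catheter failure is related to tumour drug level, so a biased go decision cannot be claimed.
- **Replacement.** Sections 8.2 and 3.3.2 conflict directly on *will* versus *may*, and by implication on toxicity.
- **Laboratory rule (minor, separate).** As written, no low value can be an adverse event. The effect is confined to adverse-event counts.

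The bounds assume that the excluded patients have assayable HGG tissue and that the evaluable five are filled by replacement.

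**What to change.** 1. In Sections 8.2 and 8.3, apply the catheter condition and the 7-of-9 rule to the dialysate endpoints only.
2. Analyse tissue endpoints in all patients, treated and control, who have HGG research tissue. Flag those who were dose-reduced, stopped or incompletely dosed.
3. Keep the 2-of-5 criterion on the evaluable five and report the all-tissue drug level beside it.
4. Reconcile Sections 8.2 and 3.3.2 into one replacement rule that says what happens after a toxicity stop.
5. In the same edit, state whether one to three missed doses meet the dosing condition, and cross-refer successful implantation to the imaging check in 7.2.1, 7.2.4 and 7.2.5.
6. Separately, reconcile the laboratory exemption in 7.2.2, 7.2.5 and 18.2 with the CTCAE v5.0 grading in 1.3 and 8.3 and the investigator review in 18.3. State how low values and non-liver analytes are handled.

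The cost is wording in these sections and possibly a few more adverse-event records. It needs no extra patients, visits or samples.
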